## LIST OF ABBREVIATIONS

AE	Adverse Event
CFR	Code of Federal Regulations
CIN	Cervical Intraepithelial Neoplasia
CRO	Clinical Research Office
CRC	Clinical Research Review and Monitoring Committee
CRF	Case Report Form
CTC	Common Toxicity Criteria
DHA	Dihydroartemisinin
DNA	Deoxyribonucleic Acid
E7	Human Papillomavirus E7 antigen
FDA	Food and Drug Administration
GCP	Good Clinical Practice
HSIL	High grade squamous intraepithelial lesion
HCG	Human Chorionic Gonadotrophin
HIPAA	Health Insurance Portability and Accountability Act
HLA	Human Leukocyte Antigen
HPV	Human Papillomavirus
IC 50	Concentration providing 50% inhibition
IM	Intramuscular
IND	Investigational New Drug Application
IRB	Institutional Review Board
IV	Intravenous
JHH	Johns Hopkins Hospital
IND	Investigational New Drug
LEEP	Loop Electrocoagulation Excision Procedure
LSIL	Low grade squamous intraepithelial lesion
PCR	Polymerase chain reaction
SAE	Serious Adverse Event
TID	Three Times A Day
WHO	World Health Organization

## 1.0 SYNOPSIS

Study drug	Artesunate
Title	A Phase I study of intravaginally administered Artesunate In women with High Grade Cervical Intraepithelial Neoplasia (CIN2/3)
Indication	Female patients, 18 years and older, with CIN2/3
Study population	Women with biopsy-confirmed CIN2/3 with a visible lesion after biopsy
Rationale	
Despite the approval of prophylactic vaccines which prevent infection with HPV types 16 and 18, the genotypes most commonly associated with squamous cancers, disease remains very common, even in high-resource settings, and is likely to remain so for decades. Infection with a high-risk HPV type is necessary but not sufficient for the development of squamous cervical cancer (SCCx) and its precursor lesion, high grade cervical intraepithelial neoplasia (CIN2/3). Both SCCx and CIN2/3 are associated with functionally obligate expression of two viral proteins, E6 and E7. Epithelial cells that express either or both of these oncoproteins also overexpress the transferrin receptor, and have increased levels of intracellular iron, compared to normal cells [1]. This observation raised the possibility of treating preinvasive HPV disease (i.e., CIN2/3) with an effective anti-malarial drug, Artesunate. Artesunate contains an endoperoxide bridge that reacts with intracellular ferrous iron to generate free radicals, leading to cell death [2, 3]. Artesunate, formulated as a suppository, is WHO-approved for first-line treatment for acute malaria in children who are remote from health care settings [4]. The toxicity profile of this formulation is well-documented. Preclinical data suggest that Artesunate mediates cytotoxic effect on HPV-infected cells, while having no effect on normal epithelium. Thus, it is proposed to investigate the use of Artesunate formulated in suppositories applied intravaginally to treat CIN2/3.

Evaluation Criteria	Safety will be assessed by the absence of related dose limiting adverse effects. Subjects will be monitored at each visit for the appearance of erythema; itching, burning, pain; infection; desquamation; tenesmus; bleeding; dizziness; or other unexpected AEs. Circulating blood cells will be monitored weekly for any quantitative changes.

Efficacy will be determined by the presence/absence of HPV, by viral load, and by regression of lesions. The presence of HPV will be determined by DNA tests before pre- and post-treatment. Histologic endpoints will be assessed with colposcopically-directed biopsies obtained before and after treatment with topical Artesunate.

In this population, it is feasible to directly visualize, serially quantitate, and perform therapeutic resection of premalignant lesions. By comparing immunologic parameters in the peripheral blood (systemic) compartment with measures obtained from the site of the lesion, pre- and post-drug administration, we expect to derive insights which will inform immune therapeutic strategies for incipient malignancies.

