of rectal artemisinin derivative (Artesunate, artemisinin and artemether) therapy [61]	achieve >90% parasite reductions at 24 hours than were multiple lower doses of rectal Artesunate, or a single lower dose administration of rectal artemether.	artemisinin-treated patients, compared with 22% of quinine-treated patients. Majority of the possibly drug-related adverse events involved either the gastrointestinal system or were generalized and non-specific in nature and were not severe.
IV Administration of Artesunate in US Phase I safety trial [51]	Dose escalation of single dose of 0.5, 1, 2, 4, or 8 mg/kg over 2 min	No dose-limiting toxicity
IV Administration of Artesunate in a Phase 1b Study [50]	3 days @ 2, 4, or 8 mg/kg over a 2-min infusion	
 
• No subject drop-outs for adverse events or other treatment-related issues.
 
• Dose-related decrease in reticulocyte count noted that peaked 4 days after dosing and returned to normal by study day 7 in most cases, and day 10 in all patients.
 
• No other clinically significant laboratory abnormalities detected.
 
• No deleterious hemodynamic or ECG effects
 
• A transient, reversible sensation of altered or unusual taste, lasted 30 minutes in all cases at higher doses of Artesunate
 

IM Administration of Artesunate in Children with Severe Malaria [54]	IM 2.4 mg/kg at 0, 12, and 24 h in children from 6 months to 11 years old	No direct report of treatment-specific complications
Comprehensive review of clinical pharmacology following administration of Artesunate by the	IV Route 
 
• High initial plasma concentration subsequently declined rapidly with a half-life of less than 15 min. Clearance and volume estimates averaged 2 - 3 L/kg/hr and 0.1 - 0.3 L/kg, respectively.
 
• The metabolite DHA concentrations peaked within 25 minutes post-dose, and a half-life of 30 - 60 minutes.
 
	

Route of Administration	Dosing Regime	Toxicity Summary

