#### **5.0 RATIONALE FOR CLINICAL TRIAL DESIGN**

This trial is a prospective, open, dose-escalation study of topical Artesunate, formulated as a suppository, administered intravaginally, prior to standard therapeutic resection of the squamocolumnar junction at study week 15. An initial dose cohort of 3 subjects will receive intravaginal Artesunate for one 5-day treatment cycle. Based on clinical experience with Artesunate, we expect that absorption in the cervical mucosa, which is stratified squamous epithelium, will be less than what is observed with rectal administration, which is a single layer of glandular epithelium. Because cervical stroma is much less vascularized than colorectal stroma, we also expect significantly lower systemic levels of Artesunate in subjects receiving intravaginal dosing. The goal of topical administration is to achieve local, mucosal distribution of study drug, as opposed to systemic levels.

If we do not observe untoward side effects, including mucosal excoriation, in the first dose cohort, we will proceed with dose-escalation. The subsequent cohort will undergo two cycles of treatment, spaced at 2-week intervals. The final cohort will undergo a total of three cycles of treatment, spaced at 2-week intervals. All subjects will undergo an interval colposcopic exam at study week 6. At week 15, if there is still a colposcopically detectable lesion, subjects will undergo standard therapeutic resection. If no lesion is obvious, a biopsy will be taken at the site of the original lesion. The cohort receiving the fewest cycles of Artesunate, and showing therapeutic effect will be expanded (see Section 12 for details). At each vaginal exam, cervical swabs will be obtained and cryopreserved. Peripheral blood will be obtained by venipuncture at baseline, and at study weeks 5, 15, and 28, 41, and the postop visit, and will be cryopreserved for assessment of biomarkers.

This clinical cohort, healthy subjects with colposcopically-directed, biopsy-confirmed CIN2/3, was selected for safety reasons. The study protocol window (15 weeks), is within the standard of care. In pregnant women who have a cervical HSIL, the standard of care is to follow colposcopically until postpartum [7]. We and others have reported that the probability that CIN2/3 will progress in this timeframe is essentially zero [63]. In fact,

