**Table 3: Outline of Evaluation Procedures**

	-3wks	Wk 0	Wk 2 	Wk 4 	Wk 6	Wk 15	Postop **	Wk 28	Wk 41
Informed consent	X								
Artesunate dosing		X	X	X					
Vital signs	X	X	X	X	X	X	X	X	X
Cervix check			X	X	X	X			
Medical history	X								
History of disease	X								
Demographic data	X								
Diary cards (give to pt)		X	X	X		X			
Diary cards (collect from pt)			X	X		X			
Adverse events		X	X	X	X	X	X	X	X
Inclusion/exclusion criteria	X								
Colposcopy	X				X	X		X	(X)*
Pap smear	X				X	X		X	X
HPV genotyping	X				X	X		X	X
Cervical swabs	X	X	X	X	X	X	X	X	X
LEEP/Cone**						(x)		(x)	
HLA testing ***	X								
PBL for banking****	X	(X)			X	X	X	X	X
Urine HCG	X	X	X	X		X			
Optional pheresis*****									

1. Treatment Group III

2. Treatment Group IV

\* Colposcopy only if clinically-required at wk 41

\*\* if residual disease is present (the procedure can happen any time after week 15, based on the physician's clinical judgment). The Postoperative visit will take place 4 +/- 1 weeks after the LEEP/Cone procedure.

\*\*\* HLA can be done at any time during the study, not an eligibility criterion

\*\*\*\* First blood draw can be done at either the screening visit or Wk 0, prior to dosing

\*\*\*\*\* pheresis is optional and can happen any time after week 15

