### 10.3 Description of Study Visits

All clinically relevant data collected during the study procedures must be recorded first in the patient file. These data will then be transcribed into the CRF. All visits will be outpatient visits.

At the initial screening visit, in addition to undergoing a standard of care colposcopic evaluation, we will obtain cervical brush specimens for HPV typing, and peripheral blood specimens to determine HLA phenotype, HIV status, and immunologic studies. Subjects with biopsy-confirmed CIN2/3 will be enrolled into treatment cohorts as depicted in Table 4 below.

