**Table 4 – Treatment Cohorts**

Cohort	Number of patients	Dose	Treatment cycles
I	3	50 mg	1 (5 days)
II	9	200 mg	1 (5 days)
III	9	200 mg	2 (5 days each)
IV	9	200 mg	3 (5 days each)

In cohort I, at the first study visit, the subjects will be given a total of five suppositories and applicators. The first suppository will be inserted in clinic, by the patient. Patients will be given diary cards, and will return 1-2 weeks after completing the regimen, for visual assessment of the cervicovaginal mucosa.

In cohorts II-IV, the first study visit will be the same as the first study visit for the run-in cohort. Subjects will return to clinic 1-2 weeks later for visual assessment of the cervicovaginal mucosa. At study week 2, patients enrolled in cohorts III and IV will undergo a visual assessment of their cervicovaginal mucosa and will be given an additional 5 suppositories and applicators. Patients enrolled in cohort III will return to clinic 1-2 weeks later for visual assessment of the cervicovaginal mucosa. At study week 4, subjects enrolled in cohort IV will undergo a visual assessment of their cervicovaginal mucosa, and will also be given five suppositories and applicators. At study week 6, **all subjects** will undergo an interval colposcopic assessment. If their lesions do not appear to be more severe than at study entry, they will return at study week 15. At study weeks 15 and 28, all subjects will undergo colposcopic evaluation. If there is any residual colposcopically abnormal tissue, it will be removed using standard excisional procedures. Peripheral blood and cervical brush specimens will be obtained at study entry, at week 5, at week 15, and at the follow-up visits: postoperative visit, and at weeks 28 and 41.

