### **Peripheral blood samples**

Blood will be drawn at various visits as noted in the protocol for analysis of various parameters and markers. The volume of blood will vary depending on the tests to be performed.

HLA typing: one 10 ml yellow top tube

Immunology samples: approximately 50 mls of blood drawn in green top (heparinized) tubes to the tissue core.

These specimens will be separated by standard Ficoll centrifugation, and the serum and PBLs aliquoted and banked at  $-70^{\circ}\text{C}$ .

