**Toxicities and Adverse events**

**Table 5: Solicited General Signs and Symptoms**

Adverse Event	Short Name	Grade 1	Grade 2	Grade 3	Grade 4	Grade 5
Allergic reaction/hypersensitivity (including drug fever)	Allergic reaction	Transient flushing or rash; drug fever <38°C (<100.4°F)	Rash; flushing; urticaria; dyspnea; drug fever ≥38°C (≥100.4°F)	Symptomatic bronchospasm, with or without urticaria; parenteral mediation(s) indicated; allergy-related edema/angioedema; hypotension	Anaphylaxis	Death
Fever (in the absence of neutropenia, where neutropenia is defined as ANC <1.0 x 10  /L)	Fever	38.0-39.0°C (100.4-102.2°F)	>39.0-40.0°C (102.3-104.0°F)	>40.0°C (104.0°F) ≤24 hours	>40.0°C (104.0°F) >24 hours	Death
Cytokine release syndrome/acute infusion reaction	Cytokine release syndrome	Mild reaction; infusion interruption not indicated; intervention not indicated	Requires therapy or infusion interruption but responds promptly to symptomatic treatment (e.g., antihistamines, NSAIDs, narcotics, IV fluids); prophylactic medications indicated for ≤24hrs	Prolonged (i.e., not rapidly responsive to symptomatic medication and/or brief interruption of infusion); recurrence of symptoms following initial improvement; hospitalization indicated for other clinical sequelae (e.g. renal impairment, pulmonary infiltrates)	Life-threatening; pressor or ventilatory support indicated	Death

Nervous system disorder	Head aches	Mild pain	Moderate pain, limiting instrumental ADL	Severe pain, limiting self care, ADL	—	-
Nervous system disorder	Dizziness	Mild unsteadiness or sensation of movement	Moderate unsteadiness or sensation of movement, limiting instrumental ADL	Severe unsteadiness or sensation of movement; limiting self care ADL	—	-
Ear and labyrinth disorder	Tinnitus	Mild symptom intervention not indicated	Moderate symptoms, limiting instrumental ADL	Severe symptoms, limiting self care ADL	-	-

Patients will be monitored throughout the study for both known potential risks and for unexpected risks. During office visits, patients will be monitored specifically for any signs of:

- Symptoms of itching, burning, pain, warmth, or tenesmus
- Signs of skin breakdown including erythema, blistering, desquamation, ulceration or bleeding
- Neurologic symptoms
- Unexpected adverse events

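### The synopsis promises weekly blood-cell monitoring but no visit schedules a blood count, so symptom-free blood toxicity is not systematically ascertained for the dose-limiting toxicity rule

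*Combined protocol and SAP*

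**What the plan says.** The synopsis (1.0, Evaluation Criteria) lists local and systemic symptoms to be watched at each visit and then adds: "Circulating blood cells will be monitored weekly for any quantitative changes". Section 7.1, which defines the primary safety outcome, gives nearly the same symptom list without that sentence.

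The blood that is scheduled serves other purposes:

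- Section 10.3, screening: "peripheral blood specimens to determine HLA phenotype, HIV status, and immunologic studies".
- Section 10.3, after Table 4: "Peripheral blood and cervical brush specimens will be obtained at study entry, at week 5, at week 15, and at the follow-up visits".
- Section 5.0: blood is taken at baseline and then "at study weeks 5, 15, and 28, 41, and the postop visit, and will be cryopreserved for assessment of biomarkers".
- Table 3: the rows involving blood are HLA testing, lymphocytes for banking (screening or week 0, then weeks 6, 15, post-operative, 28 and 41) and optional pheresis. A footnote says "First blood draw can be done at either the screening visit or Wk 0, prior to dosing".
- Section 10.4, Peripheral blood samples: one HLA tube and heparinised immunology tubes. "These specimens will be separated by standard Ficoll centrifugation, and the serum and PBLs aliquoted and banked at" −70°C.

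Section 11.8 defines a DLT as any grade 3 toxicity in any organ system, or an allergic reaction of grade 2 or higher. Section 11.9 uses the same trigger for stopping. Section 12.1 bases escalation on DLTs seen by the cervix check after the last suppository, and 11.7 requires grading by CTCAE 4.0.

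**The concern.** Safety is the primary outcome, and the rule that calls a dose level safe covers every organ system. Symptoms reach the record through visits and diary cards. A fall in haemoglobin, neutrophils or platelets that causes no symptoms is seen only if someone takes a count, and no count is planned. A level declared safe would then have been judged without a measure that the synopsis says is being followed.

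Blood is also the system in which the protocol itself reports laboratory effects. Section 3.1 mentions transient reticulocytopenia and neutropenia with artemisinin compounds. Table 2 says of the three-day intravenous study: "Dose-related decrease in reticulocyte count noted that peaked 4 days after dosing and returned to normal by study day 7 in most cases". Cohorts are small, so one unseen DLT would change a decision. Any DLT fails the run-in condition, one in nine adds three patients, and two stop escalation.

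**Working it through.** **1. The plan's own figure.** Section 12.1 states a chance below 9% of escalating when the true DLT rate is 30%. With the rule as written (0 of 9, or 1 of 9 then 0 of 3):

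0.7^9 + 9 × 0.3 × 0.7^8 × 0.7^3 = 0.0404 + 0.0534 = 0.0937.

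Read as at most one DLT in 12:

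0.7^12 + 12 × 0.3 × 0.7^11 = 0.0850.

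The stated figure is met on the second reading and narrowly missed on the first. Both calculations assume that every DLT is observed.

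**2. Promise against schedule.** The synopsis has weekly quantitative monitoring. Table 3, 5.0, 10.3 and 10.4 contain no blood count, differential or reticulocyte count at any visit. Scheduled counts: 0.

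**3. Exposure without a count** (Table 4).

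- Cycles: 3×1 + 9×1 + 9×2 + 9×3 = 57 in 30 women.
- Cycles dispensed after an earlier one: 9×1 (cohort III) + 9×2 (cohort IV) = 27.
- Escalation steps: I to II, II to III, III to IV = 3.

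**4. Could weekly monitoring be done?** The synopsis gives no end date. Assuming weeks 0 to 6, each woman needs 7 time points. Counting the first return visit and the week 2 visit as one, cohorts I and II have 3 visits in that span (week 0, return visit, week 6) and cohorts III and IV have 4. If monitoring stopped at week 2 in the one-cycle cohorts, they would need 3 time points and have 2 visits. The schedule falls short either way.

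**5. When is blood first drawn after dosing?** With consecutive daily doses, the last dose falls on day 4 (cohorts I–II), 18 (III) or 32 (IV). Table 3 puts the next draw at week 6; sections 5.0 and 10.3 put it at week 5.

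| Draw | I–II | III | IV |
|---|---|---|---|
| Week 6 (day 42) | 42−4 = 38 days | 42−18 = 24 days | 42−32 = 10 days |
| Week 5 (day 35) | 35−4 = 31 days | 35−18 = 17 days | 35−32 = 3 days |

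These samples are banked, not counted.

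**6. Dose in context.** The trial maximum is 200 mg / 50 kg = 4 mg/kg, half the highest intravenous dose of 8 mg/kg. The multiple-dose intravenous study gave 3 daily doses; cohort IV takes 5 × 3 = 15.

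**7. Can counts fit the existing visits?** Section 10.2 lets the four remaining doses take up to 2 weeks and allows ±1 week at weeks 2, 4 and 6. In the slowest case in cohort IV, with each visit on the day after the last dose, cycle 1 runs days 0–14 (visit day 15), cycle 2 days 15–29 (visit day 30) and cycle 3 days 30–44 (visit day 45). The windows are days 7–21, 21–35 and 35–49, so all three visits fit.

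**The case against.** The strongest reply is that the synopsis sentence is a stray. Section 7.1, Table 3, 10.3 and 10.4 agree with one another, and deleting one line would make the document consistent. That is a fair reading of how the mismatch arose. Deletion would not settle the matter, because 11.8, 11.9 and 12.1 would still cover any organ system with no planned measurement for blood.

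The reassuring evidence also stands. Table 2 reports no dose-limiting toxicity after single intravenous doses up to 8 mg/kg. In the three-day study, reticulocytes recovered by day 10 in every patient and no other clinically significant laboratory abnormality was found. Section 3.1 repeats that daily intravenous boluses up to 8 mg/kg were not dose-limiting. Section 2.4.4 calls the red-cell effects mild and reversible in humans, and 3.1 and 5.0 expect lower systemic levels by the vaginal route. Against this, 3.1 acknowledges that no pharmacologic data by the vaginal route have been published.

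A reader might infer that blood toxicity could never be detected or graded. The documents do not support that. Section 10.4 lets the investigator add investigations (under Vital signs) and speaks loosely of various parameters and markers (under Peripheral blood samples). Unscheduled counts are possible; none is planned for every patient.

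Table 5 has a row headed "Fever (in the absence of neutropenia, where neutropenia is defined as ANC" below a limit, which presumes a neutrophil count. The same table has an infusion-reaction row that cannot apply to a suppository, so this may be template text and carries little weight.

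A reticulocyte count at a visit 1–2 weeks after dosing may well miss a fall that peaks at day 4, and the documents show no CTCAE grade for it. That part of the reply stands, and the fix allows for it.

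**Conclusion.** The point holds as a gap in ascertainment. The stated weekly monitoring cannot be delivered by the schedule, and symptom-free blood toxicity is not systematically looked for, although the DLT, stopping and escalation rules include it. The size is 0 scheduled counts over 57 cycles, 27 repeat dispensings and 3 escalation steps. It should be corrected, but the risk behind it is probably low.

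A reader might go further and infer that escalation is much more permissive than stated. If a quarter or a half of true DLTs were laboratory-only and unseen, the 9.4% in step 1 would become 22.4% or 45.8%. Those shares are pure assumption. The documents give no rate of blood toxicity by the vaginal route, and no human study they summarise reports a grade 3 blood toxicity. The figures show the mechanism and should not be read as an estimate.

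The intervals in step 5 assume consecutive daily dosing, and the 7 time points in step 4 assume monitoring to week 6. The finding that no count is scheduled depends on neither.

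**What to change.** - Add a complete blood count with differential to Table 3 and 10.4: once before the first dose (screening or week 0) and at the existing cervix-check visit after each cycle.
- Grade haemoglobin, neutrophils and platelets by CTCAE 4.0. Review the result before the next cycle is dispensed and, in 12.1, before a patient is counted as DLT-free.
- Where a cycle's doses are spread over up to 2 weeks, use the existing ±1 week window so that the count follows the last dose.
- Treat reticulocytes as optional and descriptive.
- Replace the weekly sentence in the synopsis with this schedule and add it to 7.1.

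Cost for 30 women: 30 pre-dose + 57 post-cycle = 87 counts. Weekly counts to week 6 would be 30 × 7 = 210. With the 12-patient expansion in 12.1 at one to three cycles, the total is 42 + 57 + 12 = 111 to 42 + 57 + 36 = 135. At the most, with 39 escalation patients (75 cycles) and a three-cycle expansion (36 cycles), it is 51 + 111 = 162, before any replaced dropouts.

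The burden is one more tube per visit and a result in hand before 27 repeat dispensings. The documents give no laboratory turnaround, so the site should confirm that same-visit results are feasible. Dose, sample size and planned cycle spacing do not change.
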